16.6 Analysis Plan

The analysis for this trial will commence at the planned time points and at the time the patients have become evaluable for the primary endpoint.

16.6.1 Primary Analysis: The primary analysis will be to estimate the difference in the complication rate (adverse cosmesis and grade 3+ toxicities) which is defined as the 24-month complication rate in experimental arm minus that in the control arm. All patients meeting the eligibility criteria who have signed a consent form and started treatment will be in the primary analysis. The complication rate will include all women evaluable at 24 months. Those who have recurrent disease or die before 24 months will not be included in this calculation. We expect that <3% of patients will not be found eligible based on failure or death.²⁴ The complication rate will be estimated using a binomial estimator in both experimental arm

and control arm, and a one-sided 90% confidence interval of the difference will be computed with normal approximation. As mentioned above, the following decisions will be made based on the 90% CI:

- ***The upper bound of the 1-sided 90% CI of the difference lies below 15%:*** The experimental arm regimen is acceptable.
- ***The upper bound of the 1-sided 90% CI of the difference lies above 15%:*** The experimental arm regimen is unacceptable.

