3.14 Pathologic Stage T0-T3N0-N1M0. (8th edition)
3.15 ECOG Performance Status (PS) 0 to 2. (Appendix I).
3.16 Able to and provides IRB approved study specific written informed consent.
3.17a Study entry (randomization) must be within 12 weeks of last surgery (breast or axilla) or last chemotherapy (if applicable).

- 3.17b Willing to return to enrolling institution for follow-up (during the active monitoring phase of the study).
- 3.18 Fair, good or excellent cosmesis, as determined by trained nurse assessment using the Harvard Cosmetic Scale.
- 3.19 Radiotherapy must begin within 12 weeks of the last breast cancer surgery or the last dose of adjuvant chemotherapy.
- 3.20 Breast conserving surgery and indications for whole breast radiotherapy.

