5.0 Stratification Factors

- 5.1 Treatment modality: Photons vs. spot scanned proton therapy. Of the total 110 patients in this study, fifty-five would be treated in each arm. We will

allow a maximum of 28 patients per arm per treatment modality (photons/x-ray or protons).

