6.2 Randomization Procedures

6.21 The factors defined in Section 5.0, together with the registering membership, will be used as stratification factors.

6.22 After the patient has been registered into the study, the values of the stratification factors will be recorded, and the patient will be assigned to one of the following treatment groups using the Pocock and Simon dynamic allocation procedure which balances the marginal distributions of the stratification factors between the treatment groups.⁵⁷

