16.0 Statistical Considerations and Methodology

- 16.1 Overview: This is an open label phase III randomized controlled trial to determine the safety of 5 fraction vs 15 fraction radiotherapy after breast conserving surgery. The goal is to determine whether the difference in 24-month complication rates between the experimental arm and the control arm is acceptable. Of interest is whether the experimental arm results in an unacceptable increase in the 24-month complication rate. If it does not, then the experimental arm will be recommended for further study. If the 24-month complication rate is found to be unacceptable, then the recommendation would be to do no further studies of the experimental arm.

- 16.2 Primary and Secondary Endpoints

16.21 Primary Endpoint: The 24-month complication rate, defined as the percentage of women evaluable at 24 months who develop one or more of the following events:

- 1) grade 3 or higher late adverse event OR
- 2) deterioration of cosmesis from excellent/good to fair/poor or from fair to poor at the 24-month evaluation (using the Harvard/NSABP/RTOG Cosmesis Scale)

16.22 Secondary Endpoints:

16.221 Acute and late adverse events including grade ≥ 2 pneumonitis.

16.223 Locoregional control, invasive disease-free, distant recurrence, disease-free survival, cause-specific survival, overall survival.

The following definitions are used for the secondary endpoints of interest:

- *Acute adverse events*: any adverse event, regardless of attribution, that occurs in the first 90 days post-RT.
- *Late adverse events* (up to 5 years post RT): any adverse event that occurred after the first 90 days post-RT and up to 5 years post-RT.
- *Ipsilateral breast tumor recurrence (IBTR)*: this is defined as local recurrence from trial registration as a first event at 5 years. IBTR is defined as both invasive and non-invasive breast cancer involving the same breast parenchyma as the original tumor.
- *Regional recurrence*: invasive breast cancer in the axilla, regional lymph nodes, chest wall, and skin of the ipsilateral breast at 5 years.
- *Distant recurrence*: metastatic cancer that has either been biopsy confirmed or clinically diagnosed as recurrent invasive breast cancer at 5 years.

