16.4 Sample Size Determination

This study requires 100 evaluable women for the primary endpoint analysis (50 evaluable patients per arm).

Ninety-two percent of expected patients completed a 3-year assessment of cosmesis in the randomized phase III study reported by Olivotto et al.⁶¹ Expected was defined as patients who were projected to have had their 3-year follow-up visit based on the date of random assignment and who did not experience recurrence, undergo mastectomy, or die. Therefore to be conservative we will anticipate enrolling 10 (5 per arm) additional patients to account for ineligibility, cancellation, major treatment violations, or other reasons. The maximum projected enrollment is therefore 110 women.

In a large randomized controlled trial Whelan and colleagues compared cosmetic outcomes between conventional and hypofractionated whole breast radiotherapy after lumpectomy. At baseline, 84% of patients in the hypofractionated arm were rated as having good or excellent cosmesis by trained nursing assessment. At 3 years, the percentage was 77%, or an absolute change of 7%.⁶² In the study proposed here, a subset of patients may receive a boost to the lumpectomy cavity which has been associated with a slightly higher risk of fibrosis and adverse cosmesis.^{63,64} Therefore, the sample size proposed for arms 1-2 is based on an assumed value of a 10% complication rate in the control arm. The rate of grade 3 or higher late toxicity in this population is expected to be $\leq 1\%$ (Whelan ASCO 2011). Since the local failure rate and death rate at 2-years in the UK start B trial²⁴ was less than 3% we assume that an additional 10% to account for patients lost to follow, failures, deaths and others should be adequate (Total enrollment of 110 patients).

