16.5 Study Decision Rule and Operating Characteristics

The primary endpoint for this trial is the 24-month complication rate. Complications will be defined as at least one of the following events: 1) grade 3 or higher late adverse event OR 2) deterioration of cosmesis from excellent/good to fair/poor or from fair to poor (using the [Harvard/NSABP/RTOG Cosmesis Scale](#))

The proposed analysis would be to compute the difference in the 24-month complication rate between the experimental arm and the control arm. A one-sided 90% confidence interval (with the upper bound of the interval) was computed by assuming a 10% complication rate in the control arm and a 15% “non-inferiority margin” of the difference (i.e. the maximum the difference can be between the experimental arm and control arm, the largest difference we’re willing to accept). The decision rule would be of the following:

- *Upper bound of the one-sided confidence interval (CI) for the difference (experimental arm 24-month complication rate minus control arm 24-month complication rate) lies above 15% then **recommend that the experimental arm is not investigated further**. The 24-month complication rate of the experimental arm is unacceptably high.*
- *Upper bound of the one-sided confidence interval (CI) for the difference (experimental arm 24-month complication rate minus control arm 24-month complication rate) is less than 15% then **recommend that the experimental arm undergo further investigation**. The 24-month complication rate of the experimental arm is potentially acceptable.*

With 100 evaluable patients, this study has 80% power with a 1-sided alpha of 0.05 to test a null hypothesis that the control arm complication rate is 10% and experimental arm control rate is 25% versus an alternate hypothesis that the complication rate in both arms is 10%. Sample size was computed using PASS v.15 software.

Other considerations: Adverse events, quality/duration of response, and patterns of treatment failure observed in this study, as well as scientific discoveries or changes in standard care will be taken into account in any decision to terminate the study.

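### Stratifying the primary risk difference by nurse-scored starting cosmesis is a near-free gain in precision and interpretability; the crude analysis is valid without it

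*Combined protocol and SAP*

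**What the plan says.** - **Event.** Section 16.21 counts a grade 3 or higher late adverse event, or "deterioration of cosmesis from excellent/good to fair/poor or from fair to poor at the 24-month evaluation". Sections 2.1.1 and 16.5 use the same transitions.
- **Weight of the components.** Section 16.4 assumes a 10% complication rate in the control arm. "The rate of grade 3 or higher late toxicity in this population is expected to be" at most 1%. Cosmesis therefore drives the endpoint.
- **Starting score.** Criterion 3.18 requires "Fair, good or excellent cosmesis, as determined by trained nurse assessment using the Harvard Cosmetic Scale". Women starting at poor are not eligible.
- **Allocation.** Section 5.0 lists one factor, "Treatment modality: Photons vs. spot scanned proton therapy". Section 6.21 adds that this factor, "together with the registering membership, will be used as stratification factors". Starting cosmesis is not among them.
- **Primary analysis.** In 16.6.1, "The complication rate will be estimated using a binomial estimator" in both arms, and "a one-sided 90% confidence interval of the difference will be computed with normal approximation". The regimen is acceptable if the upper bound is below 15 points and unacceptable if it is above.
- **Baseline description.** Section 12.0 does not list starting cosmesis among the descriptive factors. Section 16.632 summarises baseline fair or poor cosmesis by arm only for the patient and panel ratings, although 11.3.1 makes the nurse rating the primary one.

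**The concern.** The distance a woman must fall to count as an event depends on where she starts. From excellent she must drop two levels, because excellent to good does not count. From good or from fair she must drop one. Any woman can also be an event through a grade 3 or higher late adverse event, but that is expected to be rare. It is therefore plausible that complication risk differs by starting category, with women who start good at higher risk than women who start excellent.

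If so, a chance excess of good starters in one arm of 50 moves that arm's rate without any effect of treatment. The decision is binary, and 16.1 says that an unacceptable result ends study of the regimen, so a result near 15 points would be hard to interpret. The plan has no table of nurse-scored baseline cosmesis by arm and no adjusted or sensitivity analysis of the primary endpoint. The trial is open label, so whether to adjust for a visible imbalance would be decided after outcomes had begun to be known.

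**Working it through.** **Step 1. The plan's own figure.** Section 16.5 states: "With 100 evaluable patients, this study has 80% power with a 1-sided alpha of 0.05", with 10% in both arms under the alternative and a 15-point margin. The unpooled normal approximation gives n per arm = (1.645 + 0.842)² × (2 × 0.10 × 0.90) / 0.15² = 49.5, so 50. At 50 per arm the standard error is √(2 × 0.10 × 0.90 / 50) = 6.0 points, and power is Φ(0.15/0.06 − 1.645) = 80.4%. The stated size is reproduced, and stratifying does not change it.

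The decision rule uses a 90% bound, not the 95% bound that alpha 0.05 implies. That is a separate matter. The steps below follow the rule as written (z = 1.2816).

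**Step 2. Sensitivity near the boundary.** Take 5/50 events in the control arm.
- 8/50 experimental: difference 6 points, SE √(0.10 × 0.90/50 + 0.16 × 0.84/50) = 6.70 points, bound 6 + 1.2816 × 6.70 = 14.6. Acceptable.
- 9/50 experimental: difference 8 points, SE 6.89 points, bound 16.8. Unacceptable.

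One event moves the bound by about 2.3 points.

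**Step 3. Size of a chance imbalance.** Section 16.4 cites a trial with 84% good or excellent at baseline. Taking the other 16% as fair (an assumption), the chance difference in fair share between arms has SD √(2 × 0.16 × 0.84 / 50) = 7.3 points. With an assumed risk gap of 10 points between fair and the rest, a 1 SD imbalance shifts the risk difference by 0.073 × 10 = 0.7 points. With a 20-point gap, a 1.96 SD imbalance shifts it by 2.9 points. The sampling standard error is 6.0 points.

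**Step 4. Crude against stratified.** Trials were simulated with 50 per arm, comparing the crude rule with a Mantel-Haenszel risk difference (Sato variance) stratified by excellent, good and fair, using the same bound and margin. Assumed shares are 40/44/16%; the excellent/good split is not in the documents. Assumed control risks by category, also not in the documents:
- none: 9.8% in every category
- moderate: 3/17/7%; overall 0.40 × 3 + 0.44 × 17 + 0.16 × 7 = 9.8%
- steep: 2/20/3%; overall 0.40 × 2 + 0.44 × 20 + 0.16 × 3 = 10.1%

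| Gradient | SE crude → stratified, equal arms | Verdicts differ: equal arms | 1.5 × risk | 1.8 × risk |
|---|---|---|---|---|
| None | 0.0594 → 0.0601 (+1%) | 2.0% | 3.9% | 4.0% |
| Moderate | 0.0594 → 0.0587 (−1%) | 3.6% | 8.2% | 8.9% |
| Steep | 0.0604 → 0.0585 (−3%) | 4.6% | 10.6% | 11.3% |

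Repeat runs agree to within about 0.2 points.

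**Step 5. Net effect.** The first row is disagreement from the change of method alone. Subtracting it leaves 1.6 to 2.6 points at equal arms (3.6 − 2.0; 4.6 − 2.0) and 4.3 to 7.3 points at higher risk (8.2 − 3.9; 11.3 − 4.0).

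**Step 6. Error rate.** At 2.5 times the risk, a true difference of 1.5 × 9.8 = 14.7 points, acceptance under the moderate gradient is 11.3% crude and 11.5% stratified. Exact enumeration of the crude rule at 10% v 25% gives 10.5% against a nominal 10%, and in simulation it stays at 10.4 to 10.6% whatever the gap between categories.

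**The case against.** The strongest reply is that nothing in the plan is wrong. An unadjusted risk difference is a legitimate prespecified primary analysis. Under randomisation, chance imbalance is part of the sampling variation that the crude interval already covers, and Step 6 confirms this. That stands in full. A reader might infer that imbalance biases the result or makes wrong acceptance more likely; the calculations show neither.

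A reader might also infer that risk differs by starting category by construction. The definition fixes the number of levels to be crossed, not the probability of crossing them. Good to fair and fair to poor are both one-level falls, and the documents give no risk by category. A gradient is plausible, not shown.

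Nor does a changed verdict mean a corrected one. With equal arms and the moderate gradient, the crude rule alone accepts in 1.7% of trials and the stratified rule alone in 1.9%. About half of the disagreement in that scenario arises with no gradient at all.

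Two practical objections remain. The fair stratum is small: 0.16 × 50 = 8 women per arm and 8 × 0.07 ≈ 0.6 expected control events. Pooling across strata with a Sato variance copes with this, but little information comes from that stratum. More important, footnote 9 in Section 4.0 lets some pre-treatment assessments be done up to 3 days into treatment. The row labels are damaged in the available text, but the row carrying footnote 9 also carries footnote 13, which concerns the cosmetic assessment. A score taken after open-label allocation would be a poor stratifier, so the plan must say which score is meant.

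What survives is the case for settling the adjustment before outcomes are seen.

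**Conclusion.** The point holds as a free or near-free improvement in precision and interpretability. It is not a flaw in validity. The crude rule keeps its error rate, and 50 per arm remains the right number for the stated design.

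The gain in standard error is about 1 to 3% under the assumed gradients and turns into a loss of about 1% if risk does not differ by starting category. The effect on the verdict, net of the change of method, is about 1.5 to 7 points of disagreement and is confined to results near the 15-point boundary. These sizes rest on assumed category shares and risks and would change with them. That the threshold depends on starting category, and that the entry score goes unused, rest on the documents alone.

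The stronger statement, that chance imbalance in starting cosmesis will decide this trial, is not supported. In most simulated trials both analyses give the same answer.

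**What to change.** In 16.6.1, prespecify a Mantel-Haenszel risk difference stratified by nurse-scored starting category (excellent, good, fair), with a Sato-type variance and the same one-sided bound and 15-point margin. Keep the crude difference as supportive. If the sponsor prefers the crude difference as primary, name the stratified estimate as a prespecified sensitivity analysis.

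Define the stratifier as the score recorded for eligibility under 3.18 before randomisation, so that a score taken under footnote 9 after treatment has started cannot be used. Add a table of nurse-scored baseline cosmesis by arm.

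The cost is a few lines of plan text, one stratified calculation and one table, with no extra patients and no new data. The downside is the loss of about 1% in precision if there is no gradient.

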4.0 Test Schedule

	Baseline	Pre-treatment	EOT	Observation ¹²			
	≤120 days prior to start of treatment	≤45 days prior to start of treatment ⁶	Last day of Treatment (+/- 5 days)	12 weeks (+/- 4 weeks) post-treatment	6 months (+/- 2 months)	12 months (+/- 3 months), 24 months (+/- 6 months), 36 months (+/- 6 months), 48 months (+/- 6 months) and 5 years (+/- 6 months) post completion of treatment	Failure*
Consent	X						
Physical exam ¹	X						
Exam/ECOG							
Visit (see Appendix)	X		X ⁸	X		X	X
Visit (see Section)		X ⁹	X ⁸	X		X ¹³	X
Visit ³		X	X	X		X	
Visit (sites 2,3,4) ¹¹		X ⁹	X	X	X	X	X
Visit (see)		X ⁹	X	X		X	X
Specimens							
Initial specimen	X ⁵						X ²
							X ⁷

1. A general history & physical exam should include height and weight (optional at Rochester site)
2. Review of pathology at failure if obtained clinically
3. Photographs can be done at any time before or after treatment at the discretion of the physician
4. Last day of treatment +/- 2 days per discretion of treating physician
5. Outside pathology must be reviewed at treating institution to confirm eligibility within 365 days.
6. Blood pregnancy test to be completed prior to start of treatment on day 1 (for women of childbearing potential only).
7. PET Scan at failure optional
8. Per discretion of treating physician for Arm 2 (5 days)
9. These tests can be done before or up to 3 days into treatment
10. Limited physical exam to include ECOG; weight (optional for Rochester site)
11. As collected clinically
12. Patients that cannot come back to Mayo within the time constraints of the follow-up schedule; efforts to obtain outside records and complete QOL's will occur, however the required items may not be captured.
13. If follow up visit occurred at an outside institution, Cosmetic Assessment will not be required.

*Failure defined as recurrent disease

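### Should the primary decision bound in 16.6.1 be a Miettinen-Nurminen score bound rather than a normal approximation?

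*Combined protocol and SAP*

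**What the plan says.** Section 16.6.1 estimates each arm's complication rate with a binomial estimator, takes experimental minus control, and states that "a one-sided 90% confidence interval of the difference will be computed with normal approximation". The regimen is acceptable if the upper bound is below 15% and unacceptable if it is above. Under 16.5 the same comparison only leads to a recommendation for or against further investigation.

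The text does not say whether the variance is pooled or unpooled, and it names no score or exact alternative.

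On sizing, 16.4 requires 50 evaluable women per arm and says that "the sample size proposed for arms 1-2 is based on an assumed value of a 10% complication rate in the control arm". Section 16.5 adds that "this study has 80% power with a 1-sided alpha of 0.05", for 10% in both arms against 10% versus 25%. On evaluability, 16.4 says "we will anticipate enrolling 10 (5 per arm) additional patients" and 16.6.1 says "The complication rate will include all women evaluable at 24 months". Footnote 13 to the Test Schedule (4.0) says "If follow up visit occurred at an outside institution, Cosmetic Assessment will not be required".

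**The concern.** The bound is the whole decision rule, so its error rate is the trial's error rate. A normal-approximation (Wald) bound estimates its variance from the observed rates. When events are few that variance tends to be too small, the upper bound sits too low, and acceptance comes too easily. In a safety comparison that is the less cautious direction.

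Three features of this plan sharpen the worry. The variance is unnamed. The 10% control rate is an assumption, and a lower rate makes the approximation worse. The arms may well not finish at exactly 50 and 50, because evaluability is known only at 24 months and cosmesis need not be assessed at outside visits. A Miettinen-Nurminen (MN) bound takes its variance at the margin itself, is in standard software and needs no new data.

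**Working it through.** **Inputs.** 50 evaluable per arm and a 10% control rate (16.4). Margin 15 points, null rates 10% and 25%, alternative 10% in both arms, alpha 0.05 (16.5). One-sided 90% bound by normal approximation (16.6.1).

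**The plan's own figure.** SE = √(2 × 0.10 × 0.90 / 50) = 0.06, and 0.15 / 0.06 = 2.5.
- Power at one-sided 0.05 = Φ(2.5 − 1.645) = Φ(0.855) = 80.4%. Exact enumeration gives 80.6%, so the stated 80% is reproduced.
- Power at the 90% bound = Φ(2.5 − 1.2816) = Φ(1.218) = 88.8% (exact 89.1%).

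**Does the unnamed variance matter?** Enumerating all 51 × 51 = 2,601 outcomes at 50 per arm, the pooled and unpooled forms give the same call every time, at both levels. An analyst could use either and reach the same decision.

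**Wald against MN.** Accept when the upper bound is below 15%.
- Wald bound: (p₁ − p₀) + z√[p₁(1 − p₁)/n₁ + p₀(1 − p₀)/n₀].
- MN: score statistic with rates constrained to differ by 15 points, variance multiplied by N/(N − 1).
- Error is evaluated at 25% versus 10%, power at 10% versus 10%.
- The averaged rows assume that each of 55 women per arm is independently evaluable with probability 50/55. This assumption is not in the plan.

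| Level and evaluable arms | Error, Wald → MN | Power, Wald → MN |
|---|---|---|
| 90% bound, 50/50 | 10.47% → 10.28% | 89.1% → 87.4% |
| 90% bound, averaged | 10.7% → 10.0% | 88.8% → 86.9% |
| Alpha 0.05, 50/50 | 5.77% → 4.92% | 80.6% → 76.6% |
| Alpha 0.05, averaged | 5.7% → 4.9% | 80.7% → 76.3% |
| Alpha 0.05, 55/55 | 5.64% → 4.77% | 84.1% → 79.3% |

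At alpha 0.05, MN reaches 80% power at 56 per arm (81.3%). That exceeds the 55 per arm the plan would enrol, even if every woman were evaluable.

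**Which decisions change?** At 50/50 and the 90% bound, 6 of 2,601 outcomes differ (experimental/control events): 5/1, 6/2, 13/11, 39/37, 48/44 and 49/45. The last three need at least 37 complications among 50 controls. As an example, 6/2 gives a difference of 0.08 and SE = √[(0.12 × 0.88 + 0.04 × 0.96)/50] = √0.00288 = 0.0537. The Wald bound is 0.08 + 1.2816 × 0.0537 = 14.9%, which accepts; MN does not. At the planned rates the two rules disagree with probability 0.19% when the experimental arm is truly 15 points worse and 1.7% when the arms are equal. At the design point, then, switching mostly rejects a regimen that is no worse.

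**Lower control rates (assumed, not the plan's), 50/50, 90% bound.**
- 7% control: error 11.2% → 10.5%, power 95.0% → 92.2%.
- 5% control: error 12.1% → 10.0%, power 97.8% → 95.8%.

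**The case for a change.** The best case for changing rests on robustness. Control complications may be rarer than 10%, and under the assumption above exactly 50/50 has only a 3.4% chance. Averaged over evaluable counts, MN stays at 9.8% to 10.0% for control rates of 5% to 15%, while Wald reaches 11.7% at a 5% control rate. Over splits from 45/55 to 55/45 and control rates of 5% to 15%, MN is closer to nominal in 48 of 55 cases at the 90% bound and 50 of 55 at the 95% bound. At 50/50 every disagreement is Wald accepting where MN rejects. Part of Wald's 80.6% power is also bought by running at 5.8% error rather than 5%.

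All of that stands as a description of the two methods. It does not show a defect in the plan. At the one design point the plan commits to, Wald is half a point above nominal and MN is also above it. MN is not always closer: with 53 experimental and 47 control women at a 10% control rate, it gives 9.2% against Wald's 9.8%. Nor is it the cheapest route to nominal error at the planned rate. In the same averaging at the 90% level, a slightly stricter normal bound (z = 1.33) has 9.9% error and 87.8% power, against 10.0% and 86.9% for MN. What MN adds is calibration at other control rates; at 5%, the stricter normal bound still has 10.8% error. Paying power for that protection is a matter of judgement.

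**Conclusion.** No change follows. The method is standard, the rule is unambiguous, the missing variance form cannot alter a decision at 50 per arm, and error at the design point is 10.5% against 10%. At the planned control rate MN would save 0.2 to 0.9 point of error for about 2 points of power at the 90% bound and 4 to 5 points at alpha 0.05. At alpha 0.05 that puts power below the stated 80% even with all 110 women evaluable. For a rule that only decides whether to recommend further study, careful statisticians could choose either bound.

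This rests on a control rate near 10% and roughly equal arms. If complications prove much rarer, the analysts can show a score bound beside the planned one without altering the rule.

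The inconsistency between the 90% bound in 16.5 and 16.6.1 and the alpha of 0.05 in 16.5 is a different point. It moves exact error from 5.8% to 10.5%, far more than the choice of interval, and changing the interval would not resolve it.
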